Gut Microbiota Dependent and Independent Impacts of Dietary Pulses on Pre- and Postprandial Metabolism and Inflammation in Overweight/Obese Humans

NCT04283448

Study Protocol and Statistical Analysis Plan

Study Document Date : 10/22/2024

Background and Objectives

Pulse crops have unrealized potential to improve health and reduce disease burden for type 2 diabetes (T2D), cardiovascular diseases (CVD), and others. There is a 2-4-fold risk of CVD in individuals with T2D, and the CDC reported that 9% have diabetes (vast majority are T2D) and 34% of US adults have prediabetes. Postprandial TG predict risk of T2D and CVD as well or better than static biomarkers such as fasting glucose or lipids and are causally linked to low-grade inflammation, which plays a direct role in the progression of T2D, CVD, and other diseases. Thus, postprandial TG and inflammation are high impact targets for disease prevention and treatment. Dietary pulses have established potential to lower disease risk through these mechanisms, but it is likely that interindividual differences in the gut microbiome influence this potential.

Diet and gut microbiota interactions are an emerging area of study. Differences in the gut microbiome may limit or enhance health benefits of pulse consumption, e.g. lowering of postprandial TG and inflammation responses. There is large inter-individual variability in which of >1,000 potential gut microbial species are present, relative abundance of each, and overall function in each individual human host. Makeup of the gut microbiome influences short chain fatty acid production from prebiotic fibers and lipid absorption, which in turn exert lipid lowering effects. Our research group has identified several bacterial groups in the gastrointestinal tract that differ in individuals with lower versus high triglyceridemic responses to a high-fat meal challenge. Changes in the gut microbiota (the community of microorganisms in the human gastrointestinal tract) and lipid lowering have been measured in animal and human research studies for lentils and black beans, but the influence of the gut microbiota changes on the lipid changes has not been determined.

Our overall goal is to determine gut microbiome dependent and independent impacts of pulse consumption on metabolic resilience and metabolic risk profiles for type 2 diabetes (T2D) and cardiovascular disease (CVD) risk. Specifically, pulse crop consumption (i.e. Peas, Dry Beans, Lentils & Chickpeas) has unrealized potential to fundamentally alter how the body responds to disease promoting metabolic stresses of postprandial triglyceride and inflammation responses. Our specific objectives are to:

1. Determine the impact of green lentil consumption on postprandial triglyceride (TG) and inflammation responses to a high-fat meal challenge.
2. Determine the extent to which the gut microbiome and changes in the gut microbiome induced pulse consumption influence health impacts
3. Measure metabolites in the blood and generate metabolomic profiles to elucidate underlying mechanisms linking pulse consumption to improved health.

To achieve these objectives, we will determine the effects of green lentils on high impact risk factors of large postprandial triglyceride excursions and inflammation, composition of and changes in the gut microbiomes, and both gut and serum metabolomes in overweight and obese individuals with elevated risk. We will introduce a 12-week intervention which will consist of

consumption of 3 cups (experimental) or 0 cups (control) of pulses per week across 7 pre-made mid-day meals (matched for macronutrient content except fiber) provided to experimental and control groups.

Study Protocol

Visits 1-4 Time Commitment: Visit 1 and 2 are expected to last less than 60 minutes. Visits 3 and 4 are both expected to last 6 hours each. Total time spent in the laboratory for these visits is approximately 14 hours.

Informed Consent: After confirming eligibility with phone interview, a copy of the informed consent document will be mailed or emailed to participants so they can read it prior to their first visit. Before the first visit, an investigator will telephone participants to discuss the procedures and risks of participation in the study and to answer questions relating to the consent document.

Visit 1:

The first 20-30 minutes of the initial laboratory visit is devoted to walking the participant through the procedures and risks of the study, as well as answering any questions they might have prior to signing the informed consent document. Participants will then be asked to complete a series of questionnaires including: a 1-page health screening (AHA/ACSM Health/Fitness Facility Preparticipation Screening Questionnaire), 1-page Physical Activity Questionnaire, and a 1-page Demographic Questionnaire (Race and Ethnicity Questionnaire). The participant will also complete a body composition analysis as described below.

Measurement of muscle and fat tissue using bioelectrical impedance analysis: This test simply involves standing on a scale with your feet and hands on sensors for a few seconds. A very low electrical current that you cannot feel and that is not dangerous is transmitted and received across the sensors. The technology is commonly used in a variety of settings such as gyms and health screenings, but the instrument that we will use is more sophisticated in being able to estimate muscle and fat tissue in different regions of your body, including the abdominal cavity that is particularly important for predicting risk of diabetes.

Visit 2:

During Visit 1, our team will work with participants to determine an appropriate meal (breakfast or lunch) to eat that contains approximately 50 g of fat and to schedule a visit (Visit 2) approximately 3-4 hours after consuming this meal. Participants will come to the lab and have blood drawn according to standard procedures, where briefly blood is collected via venous puncture from a forearm vein.

Random Assignment: Participants will be randomized into Pulse or Control groups after Visit 2 if their non-fasting serum TG concentration 3-4 hours after a meal of the participant's choosing is greater than 175 mg/dl. Individuals with non-fasting TG levels less than 175 mg/dl will not complete the 12 week dietary intervention and will receive the benefits that were a part of their conducted visits in addition to monetary payments, prorated to the their total time spent in the study.

Dietary intervention: Using methods we have established for an ongoing randomized clinical trial with 8 weeks of lentil supplementation, we will prepare 7 mid-day meals per participant per week to deliver a dose of 0 or 3 cups of lentils per week for the experimental and control groups. Meals are matched for macronutrient content (except for fiber), and ground turkey replaces lentils in the control meals. Participants will be instructed to consume food provided for their midday meal, and then to proactively reduce portion sizes and to not eat beyond fullness at the evening meal. This strategy exploits the satiety effect of pulses at the midday meal and the 'second meal effect' in which volitional consumption is reduced at the next meal, the evening meal.

A brief 4 pm online survey addressing satiety and a brief 8 PM online survey addressing gastrointestinal issues will be delivered once a week during the 12-week intervention to participants through personalized e-mails or texts. Each participant will be surveyed once weekly to determine whether they consumed the experimental meal that day, their perceptions of hunger, fullness, satiety, and satisfaction with that day's meal (at 4:00 pm), and their gastrointestinal comfort (level of bloating, flatulence, cramping, and comfort) throughout the day (at 8:00 pm). This methodology has been successfully implemented in our ongoing study to demonstrate that lentil meals are equally pleasing, produce greater satiety, and are well-tolerated.

Vist 3 and 4:

Blood collection and high fat meal. Standard procedures for collection of blood from a forearm vein will be used to collect blood. In brief, participants will report to the laboratory after an overnight fast (10-12 hours), an indwelling venous catheter will be placed in an antecubital vein by an experienced physician, nurse, or phlebotomy-trained graduate student. [name], [name], or [name], will be present and/or on-call for all catheter placements. Blood samples will be collected before, and 1, 2, 3, 4, and 5 hours following ingestion of the high-fat meal. The high fat meal is 58.3 grams of salted butter (for 50 g of dietary fat) spread over three pieces of toast. High-fat meal challenges with 40-100 g of dietary fat are an established laboratory test to measure both postprandial triglyceridemic and inflammation responses. We have used a 50 g dose of fat delivered in the form of butter on toast on > 50 individuals because this particular dose is effective at discriminating between low versus high TG and inflammation responders. During this time, participants will not be allowed to leave the laboratory area. There will be down time in between blood draws and participants will be encouraged to bring entertainment or work with them to the laboratory, of which we will assist with connecting them to the campus WiFi network. They will be allowed to consume water, but not allowed to consume additional food or drink outside of the high fat meal. From collected blood samples, we will measure inflammatory cytokines, lipids, insulin, and metabolites (small molecules relating to the biochemical process in your body).

Questionnaires. Participants will be asked to complete a 24-hour dietary recall where they outline the types and quantities of food and beverage consumed in the past 24 hours, and a food frequency questionnaire. Completion of the food frequency questionnaire takes approximately 1-2 hours and details the participants' usual diet. Participants can complete these questionnaires

during the course of their visit. An end of study questionnaire will be completed at the end of Visit 4 to elicit feedback from the participant regarding their experience as a participant.

Self-Collected Stool Sample: A stool sample will be used to analyze the types of microbes present in the gut. The analysis involves measurement of the genetic material of the bacteria. This does not give us any information about the individual's genetic material, only that of the bacteria in their gut. They will be given three self-collection kits that each come with printed step-by-step instructions to collect their stool sample. Two kits will be given at visit 2 for stool sample delivery at Visit 3. An additional kit will be given towards the end of the study in coordination with a meal pick-up for stool sample delivery at Visit 4.

Biospecimen Analysis

All blood and fecal specimens collected during Visits 3 and 4 are de-identified at the point of collection and remain de-identified for the duration of testing and analysis.

Stool samples are sent to the University of Michigan through [name] lab for 16S analysis. De-identified, un-processed, microbial DNA results are electronically sent back to MSU Nutrition Lab for data processing and analysis. Serum samples for metabolomic analysis are sent to [name] lab where de-identified results are processed and analyzed. Results are electronically sent back to MSU Nutrition Lab for additional analysis. Remaining biomarker analyses including inflammation, lipid, and blood glucose levels are processed and analyzed in the MSU Nutrition Research Lab as de-identified specimens.

All biospecimen results remain de-identified through study publication.

Statistical Plan

Habitual dietary patterns, represented by DHQ-III HEI scores, were analyzed at base-line through general linear models to detect existing dietary differences between meal groups. Diet components expected to change with a lentil-based intervention including total fiber g, insoluble fiber g, and legumes (cups) as well as total energy intake (kcals) were also assessed for baseline differences. To determine if intervention meal consumption changed participant dietary intake, linear mixed effects models were used to assess dietary components and HEI scores with an interaction predictor between meal and time (pre- or post- intervention) and a random effect for subject. Post-hoc multiple pairwise comparisons were performed to detect significant differences by group using Tukey's HSD.

Linear mixed effects models were used to assess the impact of a week and meal interaction on satiety measures. GI symptom severity was analyzed through a linear mixed effects model with symptom type and a week and meal interaction as predictors. Subject was the random effect for models assessing satiety and GI symptom severity.

Descriptive summary statistics were performed for participant physical and biological characteristics with general linear models used to determine if participants on average differed between meal groups before the intervention began. General linear models were used to assess

the impact of the dietary intervention on the following categories of variables: anthropometric measures (weight, fat mass percent, visceral adipose, and waist circumference); fasting blood lipid measures (CHOL, HDL, LDL, TG); fasting glycemic measures (GLU, INS, HOMA-IR); and fasting inflammation markers (GM-CSF, IFN- γ , TNF- α , IL-1 β , IL-6, IL-10, IL-17, IL-23). Fasting inflammation markers were normalized using r package bestNormalize [38] prior to statistical analysis. Dependent variables were calculated as the change in values from baseline (post-intervention – pre-intervention). Predictor variables were shared within each category of variables and are as follows: anthropometric measures –meal group; blood lipid measures –meal group, visceral adipose tissue; glycemic measures –meal group, visceral adipose tissue, change in BMI, HbA1c; inflammation measures –meal group, visceral adipose tissue. Predictor variables for glycemic measures were chosen based on previous findings by Zeevi and colleagues [39].

Analysis of postprandial metabolic (TG, GLU, INS) and inflammatory (GM-CSF, IFN- γ , TNF- α , IL-1 β , IL-6, IL-10, IL-17, and IL-23) measures were conducted by summarizing each makers measurements at timepoints 0 (fasting) and 1, 2, 3, 4, and 5 hours postprandially as net area under the curve (AUC) using the auctime [40] R package. Each dependent variable was then summarized as the change in AUC (post-intervention – pre-intervention). AUC values for inflammation markers were normalized using r package bestNormalize [38] prior to statistical analysis. General linear models were used to assess the impact of intervention meal group on each dependent variable. Predictor variables were identical to variables utilized in corresponding fasting models.

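### Randomisation is tied to the Visit 2 triglyceride result, apparently before the Visit 3 baseline; releasing allocation after Visit 3 would be a cheap, low-severity improvement

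*Combined protocol and SAP*

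**What the plan says.** **Timing of allocation.** Under Random Assignment: "Participants will be randomized into Pulse or Control groups after Visit 2", provided the non-fasting TG exceeds 175 mg/dl. No other condition is given, and no latest time. The text then moves to the dietary intervention and after that to Visits 3 and 4.

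**Where the baseline comes from.** The fasting sample and the challenge-meal series are described only for Visits 3 and 4: "Blood samples will be collected before, and 1, 2, 3, 4, and 5 hours following ingestion of the high-fat meal". The dietary recall and food frequency questionnaire are also completed at those visits. The stool-sample section places Visit 3 at the start ("Two kits will be given at visit 2 for stool sample delivery at Visit 3") and Visit 4 at the end, with the last kit handed out late in the study "in coordination with a meal pick-up for stool sample delivery at Visit 4".

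**How outcomes are formed.** The Statistical Plan says of the fasting measures: "Dependent variables were calculated as the change in values from baseline". Postprandial measures are summarised as net AUC and then as the post-minus-pre change in AUC. Both are analysed with general linear models. No imputation rule or analysis population is stated.

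**Visit burden.** "Visit 1 and 2 are expected to last less than 60 minutes. Visits 3 and 4 are both expected to last 6 hours each".

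**The concern.** A participant allocated on the Visit 2 result who never completes Visit 3 has no pre-intervention fasting value and no pre-intervention AUC, and so no change score. That person was randomised but cannot enter the analysis of postprandial TG and inflammation, which is Objective 1. The same loss occurring before allocation would be an ordinary screening loss and would leave the randomised comparison intact.

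Some loss at this step is plausible. Visit 3 is the first 6-hour visit, and the first to require an overnight fast and an indwelling catheter. If participants already know their arm, the decision to attend could depend on it. The baseline dietary questionnaires, which are self-reported, could then also be answered with the arm in mind.

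**Working it through.** The documents give no sample size, loss rate, effect size or disclosure time, so there is no design figure on this point to reproduce. The one related figure, total visit time, agrees with the stated approximate total: 1 + 1 + 6 + 6 = 14 hours.

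**Step 1: can Visit 2 stand in for Visit 3?** Visit 2 gives one non-fasting TG, 3 to 4 hours after a self-chosen meal of roughly 50 g fat. The outcome needs samples at 0, 1, 2, 3, 4 and 5 hours after a standard meal. One value cannot supply a fasting level or an AUC. Visit 3 is therefore the only pre-intervention source of both.

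**Step 2: what happens without Visit 3?** Change = post minus pre. With no pre value and no stated imputation, the dependent variable is undefined and a general linear model on one change score per person omits the participant. This follows from the definitions; the plan does not say it in words.

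**Step 3: size of a possible bias (all inputs assumed).** Let L be the extra loss in one arm and d the difference in mean change between those lost and those retained, in SD units. The mean of those retained differs from the mean of everyone in that arm by L × d, so the contrast between arms is biased by L × d.

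- Smallest case: 0.05 × 0.25 = 0.0125 SD.
- Largest case: 0.10 × 0.5 = 0.05 SD.

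Set against the standard error, SE = √(1/n + 1/(n(1−L))) in SD units, with n per arm:

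| n per arm | Bias/SE, smallest case | Bias/SE, largest case | Rejection of a true null at nominal 5%, largest case |
|---|---|---|---|
| 20 | 0.039 | 0.154 | 5.3% |
| 30 | 0.048 | 0.188 | 5.4% |
| 40 | 0.055 | 0.218 | 5.5% |
| 50 | 0.062 | 0.243 | 5.7% |

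For example, at n = 50 and L = 0.10, SE = √(0.02 + 0.0222) = 0.2055, and 0.05/0.2055 = 0.243. In the smallest case the rejection rate stays at 5.0% throughout. If loss is equal in both arms and d is the same in both, the bias is 0.

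**Step 4: power.** Suppose 60 people pass the TG screen and 10% miss Visit 3. Then 60 × 0.9 = 54 are available for analysis whether allocation comes before or after Visit 3. The order changes precision only if the recruitment target counts randomised participants, so that late allocation leads to the lost people being replaced. No target is stated.

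**Step 5: diet.** If baseline reports in one arm shift by s SD, the meal-by-time contrast for diet shifts by s SD in magnitude. The documents give nothing from which to set s. This analysis has a supporting role: its stated purpose is "To determine if intervention meal consumption changed participant dietary intake".

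**The case against.** **The order is not stated.** Allocation after Visit 3 would also be allocation after Visit 2, so the proposed order is already compatible with the text. This stands, and it is why the point is worded as the natural reading only. Even so, the only trigger given is the Visit 2 result, and Visit 3 is never mentioned as a condition.

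**Any bias needs a chain of undocumented conditions.** Allocation must precede Visit 3, the arm must be known by then, people must be lost, the loss must differ by arm, and it must relate to outcome. This also stands. The visit burden is the same in both arms. The Dietary intervention section reports from an ongoing study that "lentil meals are equally pleasing, produce greater satiety, and are well-tolerated", which points away from strongly unequal loss.

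**Visit 2 is itself a postprandial measurement.** It is, and it would allow those lost to be compared with those retained on one pre-randomisation TG. It does not replace the AUC.

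**Dietary reports are unlikely to move much.** The food frequency questionnaire asks about usual diet, which limits the room for a shift, and diet is not one of the three objectives. Both observations are fair.

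**Stronger inferences to avoid.** A reader might infer that the order costs power, that the Objective 1 comparison is in fact biased, or that the body composition baseline is affected too. The documents support none of these. The same people are lost under either order unless the target counts those randomised. No loss or early disclosure is reported. Body composition is measured at Visit 1, and the plan does not say which visit supplies its pre-intervention value.

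**Conclusion.** The point holds as a low-severity design improvement. On the natural reading, the plan allows participants to be randomised before the visit that creates their baseline for Objective 1, and anyone lost in between becomes a post-randomisation exclusion. With the arm undisclosed until after Visit 3, no arm-driven bias is expected from this source. With early disclosure and unequal, outcome-related loss, the assumed ranges give a bias of 0.01 to 0.05 SD, or 0.04 to 0.24 of a standard error at 20 to 50 per arm. These figures rest wholly on assumed inputs, and the actual number who missed Visit 3, if any, is unknown. No precision or power benefit is claimed.

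**What to change.** **If the trial is still enrolling:** keep the Visit 2 TG threshold as the eligibility screen. Generate and release the allocation only once Visit 3 samples and questionnaires are complete, and before the first meal pick-up. By construction, no one is then randomised without having completed Visit 3. This needs a one-line protocol change and adds no visit, sample or test. No procedure described for Visit 3 depends on the arm. The downside is a short wait while the allocated meals are prepared.

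**If enrolment is complete,** as the past tense of the Statistical Plan suggests: state when allocation was generated and when it was disclosed to participants and staff, relative to Visit 3. Report by arm the number randomised who did not complete Visit 3. This costs one sentence and one row in the participant flow.

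Neither version deals with participants who miss Visit 4, which needs its own missing-data provision.

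### The diet-intake mixed models leave the two pre-intervention arm means free, so the arm effect is valid but less precise than the same data allow; the baseline significance tests of randomised arms add nothing.

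*Combined protocol and SAP*

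**What the plan says.** **Allocation.** Under Random Assignment (Visit 2 section), "Participants will be randomized into Pulse or Control groups after Visit 2", subject to the triglyceride criterion.

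**Baseline comparisons.** In the Statistical Plan, baseline HEI scores "were analyzed at base-line through general linear models to detect existing dietary differences between meal groups". Total fiber, insoluble fiber, legumes, "as well as total energy intake (kcals) were also assessed for baseline differences". Physical and biological characteristics get descriptive summaries, with "general linear models used to determine if participants on average differed between meal groups before the intervention began". Those characteristics are not listed, and no significance level is given.

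**Diet effect.** For change in intake, "linear mixed effects models were used to assess dietary components and HEI scores with an interaction predictor between meal and time". Time has two levels (pre and post), and subject is a random effect. No baseline covariate or shared pre-intervention mean is mentioned. The next step is: "Post-hoc multiple pairwise comparisons were performed to detect significant differences by group using Tukey's HSD". The pairs to be compared are not named.

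**Timing of the diet measure.** The section on Visits 3 and 4 places a 24-hour recall and a food frequency questionnaire at those visits ("Participants can complete these questionnaires" while there). I take the food frequency questionnaire to be the source of the HEI scores. The pre-intervention report is then made at Visit 3, after randomisation. The plan does not say when participants learn their arm relative to that visit.

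**The concern.** Randomisation makes the expected pre-intervention difference between arms zero, provided the baseline report is unaffected by allocation. The plan spends this knowledge in the wrong place. It tests for a baseline difference, where the answer cannot help: a small p-value would reflect chance, and a large one would not show balance. It then leaves the equality unused in the diet model, where it would sharpen the estimate.

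At stake is the precision of the plan's own check that the meals changed intake. A wide interval there could be misread as failed delivery of the intervention. The unlisted Tukey comparisons make this harder to read. If all four meal-by-time cells are compared there are 4 × 3 / 2 = 6 pairs. One of them tests the arms at baseline again, and none is the difference in change.

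**Working it through.** **Inputs.** From the documents: two randomised arms, two time points, a meal-by-time interaction, a random subject effect, and five named dietary baseline tests (HEI, total fiber, insoluble fiber, legumes, energy). Not in the documents, so assumed: pre-post correlation r (0.3 to 0.9), equal allocation with n per arm (30 for illustration), two-sided alpha 0.05, and equal SD σ at both times. The plan gives no sample size or power figure to reproduce.

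**1. What the planned model estimates.** With complete data, the interaction equals the difference in mean change:

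Variance = 2 × 2σ²(1−r)/n = 4σ²(1−r)/n.

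**2. What the same data allow.** Adjusting for the participant's own baseline, or sharing one baseline mean, gives approximately:

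Variance = 2σ²(1−r²)/n.

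**3. Ratio, adjusted to planned.** 2(1−r²) / [4(1−r)] = (1+r)/2.

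| assumed r | variance multiplier (1+r)/2 | planned SE larger by | planned power when adjusted power is 80% |
|---|---|---|---|
| 0.3 | 0.65 | 24% | 62% |
| 0.5 | 0.75 | 15% | 68% |
| 0.7 | 0.85 | 8% | 73% |
| 0.9 | 0.95 | 3% | 78% |

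With unequal SDs σ₀ (pre) and σ₁ (post), the residual variances are σ₀² + σ₁² − 2rσ₀σ₁ for change and σ₁²(1−r²) for the adjusted analysis. They differ by (σ₀ − rσ₁)², which is never negative. The direction of the result therefore does not rest on equal SDs, although its size does.

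**4. Small-sample cost.** Estimating the baseline slope inflates the adjusted variance by about 1 + 1/(2n−4). At 30 per arm this is 1 + 1/56 = 1.018, so the multiplier at r = 0.9 becomes 0.95 × 1.018 = 0.967. At 15 per arm it is 1 + 1/26 = 1.038, giving 0.986.

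**5. Simulation check.** With 20,000 null trials per r at 30 per arm, the planned-to-adjusted variance ratio was 1.50, 1.30 and 1.16 at r = 0.3, 0.5 and 0.7. Inverted, these are 0.67, 0.77 and 0.86, in line with steps 3 and 4. Rejection under the null was 4.8% to 5.2% for both analyses.

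**6. One fitted example (r = 0.7).** In the planned mixed model the meal coefficient equalled the raw baseline difference (−0.169), and the interaction equalled the difference in change (−0.055, SE 0.204). With a common baseline mean the effect was −0.103 (SE 0.189). The shift is (−0.103 + 0.055)/(−0.169) = 0.28 of the baseline difference, close to 1 − r = 0.30. Both the estimate and its standard error change.

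**7. Baseline tests.** For the five named tests, 5 × 0.05 = 0.25 false positives are expected, and the chance of at least one is 1 − 0.95⁵ = 22.6% if they are independent.

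**The case against.** **The planned analysis is sound.** This stands. The interaction test is unbiased and keeps its type I error. Diet intake is a supporting outcome, not the postprandial responses of objective 1. Legumes and fiber should differ between arms by design (3 against 0 cups of pulses a week), so precision matters more for energy and HEI.

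**The gain may be small.** This also stands. With r unknown, the saving could be only 5% to 10% of variance at r = 0.8 to 0.9, and less after the small-sample cost.

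**Baseline equality is not assured.** This is the strongest objection. The diet report comes after randomisation, disclosure is undescribed, and no analysis set is defined, so people lost between Visits 2 and 3 may have no baseline. If knowing the arm shifts the baseline report, a common-mean constraint can introduce bias. Covariate adjustment leans on the same condition. The planned model imposes no such equality and cancels any shift that is the same at both visits.

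**Stronger readings the text does not support.** A reader might infer that chance baseline differences will be reported as findings or will choose covariates. The plan does not say how the test results are used, and it fixes predictors by outcome category. A reader might also count 24 baseline tests by adding the 19 anthropometric, lipid, glycemic and inflammation outcomes, for a 70.8% chance of at least one p<0.05. That list describes intervention outcomes; the characteristics tested at baseline are not itemised. Finally, deleting the baseline tests would not improve the diet model. The two changes are separate.

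**Conclusion.** The point holds as one of efficiency, with a secondary reporting point. For HEI, total fiber, insoluble fiber, legumes and energy, the planned model discards information that the trial already collects. Using it would cut the variance of the arm effect by about 35%, 25%, 15% or 5% at r = 0.3, 0.5, 0.7 or 0.9. These figures assume complete data, equal pre and post SDs, and a baseline report unaffected by allocation; r and the sample size are assumptions throughout. Nothing here shows bias or inflated error in the planned test.

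The baseline tests can establish neither imbalance nor balance. Five are named and the number of others is unstated. Removing them is good reporting practice and alters no planned estimate.

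The change-score models for fasting and postprandial outcomes also lack a term for the outcome's own baseline. That is a separate matter and is not sized here.

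**What to change.** 1. **Diet models.** Name one contrast per outcome: the post-intervention difference between arms with its 95% CI. Either adjust for the participant's own pre-intervention value, or fit time plus meal-by-post terms so that both arms share one baseline mean. Let this contrast replace the unlisted Tukey pairs as the basis for the conclusion.
2. **Condition.** State whether the Visit 3 questionnaire was completed before the arm was disclosed and before meals began, and which randomised participants are analysed. If this cannot be confirmed, keep the current meal-by-time model and say why.
3. **Baseline table.** Give means, SDs and standardised differences by arm, without p-values.
4. **Status.** The plan is written in the past tense. If results have already been seen, present the baseline-adjusted analysis as supplementary, beside the planned one.

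The cost is a few sentences of SAP text and one change of model terms, plus a check of questionnaire and disclosure dates. No new data are needed. The customary p-value column in the baseline table is lost.
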